4.2 Pembrolizumab

Pembrolizumab is a potent humanized immunoglobulin G4 (IgG4) monoclonal antibody (mAb) with high specificity of binding to the programmed cell death 1 (PD 1) receptor, thus inhibiting its interaction with programmed cell death ligand 1 (PD-L1) and programmed cell death ligand 2 (PD-L2). Based on preclinical in vitro data, pembrolizumab has high affinity and potent receptor blocking activity for PD 1. Pembrolizumab has an acceptable preclinical safety profile and is in clinical development as an intravenous (IV) immunotherapy for advanced malignancies. Keytruda® (pembrolizumab) is indicated for the treatment of patients across a number of indications because of its mechanism of action to bind the PD-1 receptor on the T cell. For more details on specific indications refer to the Investigator brochure.

4.2.1 Pharmaceutical and Therapeutic Background

The importance of intact immune surveillance function in controlling outgrowth of neoplastic transformations has been known for decades [10]. Accumulating evidence shows a correlation between tumor-infiltrating lymphocytes in cancer tissue and favorable prognosis in various malignancies. In particular, the presence of CD8+ T-cells and the ratio of CD8+ effector T cells/FoxP3+ regulatory T-cells (T-reg) correlates with improved prognosis and long-term survival in solid malignancies, such as ovarian, colorectal, and pancreatic cancer; hepatocellular carcinoma; malignant melanoma; and renal cell carcinoma. Tumor-infiltrating lymphocytes can be expanded ex vivo and reinfused, inducing durable objective tumor responses in cancers such as melanoma [11, 12].

The PD-1 receptor-ligand interaction is a major pathway hijacked by tumors to suppress immune control. The normal function of PD-1, expressed on the cell surface of activated T cells under healthy conditions, is to down-modulate unwanted or excessive immune responses, including autoimmune reactions. PD-1 (encoded by the gene *Pdcd1*) is an immunoglobulin (Ig) superfamily member related to cluster of differentiation 28 (CD28) and cytotoxic T-lymphocyte-associated protein 4 (CTLA-4) that has been shown to negatively regulate antigen receptor signaling upon engagement of its ligands (PD-L1 and/or PD-L2) [13, 14].

The structure of murine PD-1 has been resolved [15]. PD-1 and its family members are type I transmembrane glycoproteins containing an Ig-variable-type (IgV type) domain responsible for ligand binding and a cytoplasmic tail responsible for the binding of signaling molecules. The cytoplasmic tail of PD-1 contains 2 tyrosine-based signaling motifs, an immunoreceptor tyrosine-

A Phase II, Single-arm Study of Combination Pembrolizumab and Olaparib in the Treatment of Patients with Advanced Cholangiocarcinoma

Version 2.1: 17Mar2023

based inhibition motif, and an immunoreceptor tyrosine-based switch motif. Following T-cell stimulation, PD-1 recruits the tyrosine phosphatases, SHP-1 and SHP-2, to the immunoreceptor tyrosine-based switch motif within its cytoplasmic tail, leading to the dephosphorylation of effector molecules such as CD3 zeta (CD3 ζ), protein kinase C-theta (PKC θ), and zeta-chain-associated protein kinase (ZAP70), which are involved in the CD3 T-cell signaling cascade [14,16-18]. The mechanism by which PD-1 down-modulates T cell responses is similar to, but distinct from, that of CTLA-4, because both molecules regulate an overlapping set of signaling proteins [19, 20]. As a consequence, the PD 1/PD-L1 pathway is an attractive target for therapeutic intervention in [disease under study].

4.2.1.1 Preclinical and Clinical Trial Data

4.2.1.2 Non-Clinical Toxicology Summary of Results

In the 1-month and 6-month toxicology study in cynomolgus monkeys, pembrolizumab, intravenously administered once a week and once every other week respectively up to a dose of 200 mg/kg, resulted in no adverse treatment-related effects. In tissue cross-reactivity studies of pembrolizumab in human and monkey tissues, the expected on-target staining of mononuclear leukocytes membranes was demonstrated in both species. Off-target cross-reactivity staining was also noted in both species but was limited to the cytoplasm of various cell types/tissues and the stroma (extracellular connective tissue matrix), and was considered related to experimental methodological artifacts, i.e. tissue processing for IHC, which are well recognized limitations of tissue cross-reactivity studies and, thus not considered toxicologically relevant. No reproductive or developmental toxicity studies are planned with pembrolizumab. Therefore, inclusion of women of childbearing potential in clinical trials should be avoided in accordance with the study protocol and applicable regulatory guidance (e.g., ICH M3(R2): Nonclinical Safety Studies for the Conduct of Human Clinical Trials and Marketing Authorization for Pharmaceuticals).

4.2.1.2.1 Clinical Summary of Results

Clinical Pharmacology Summary

The PK profile of pembrolizumab, with low clearance and limited volume of distribution, is typical for therapeutic antibodies. Exposure to pembrolizumab is approximately linear in the dose range of clinical relevance (1 to 10 mg/kg and at 200 mg). Furthermore, pembrolizumab has a low potential of eliciting the formation of ADAs.

Efficacy Summary

For the treatment of unresectable or metastatic melanoma, pembrolizumab demonstrated superior efficacy over available treatment options (IPI, Investigator's choice chemotherapy) in participants with advanced melanoma who were treatment-naïve, as well as those who progressed on prior therapy, including IPI.

A Phase II, Single-arm Study of Combination Pembrolizumab and Olaparib in the Treatment of Patients with Advanced Cholangiocarcinoma

Version 2.1: 17Mar2023

Pembrolizumab provided substantial, clinically meaningful benefits in OS, PFS, and ORR in participants with NSCLC who progressed after platinum-containing chemotherapy and whose tumor cells expressed PD-L1. In previously treated participants with PD-L1 TPS $\geq 1\%$ and disease progression following platinum-containing chemotherapy, pembrolizumab provided a statistically significant and clinically meaningful OS benefit compared to standard docetaxel chemotherapy. For participants with previously untreated metastatic NSCLC whose tumors express high levels of PD-L1, pembrolizumab demonstrated significant improvements in PFS and OS over standard of care chemotherapy.

Pembrolizumab in combination with pemetrexed/carboplatin for the first-line treatment of metastatic nonsquamous NSCLC demonstrated both a statistically significant and clinically meaningful difference in ORR and a statistically significant benefit in PFS compared with pemetrexed/carboplatin alone.

For the treatment of advanced HNSCC in a heavily pretreated population, pembrolizumab demonstrated a clinically meaningful response rate and a prolonged duration of response that is substantially distinct from what is expected with standard of care in previously treated participants with HNSCC, and points to the meaningful clinical benefit of pembrolizumab.

Pembrolizumab for the treatment of relapsed or refractory cHL, has demonstrated durable, robust, clinically meaningful responses in this heavily pretreated population that generally included standard front-line therapies, salvage therapies, auto-SCT if eligible with chemosensitive disease, other single agent or combination chemotherapy regimens as needed, and with or without BV.

For the treatment of urothelial cancer (UC) in participants who have not received prior chemotherapy and are cisplatin-ineligible, pembrolizumab demonstrated a clinically meaningful ORR in participants with locally advanced or metastatic UC. In participants with locally advanced or metastatic UC who have received platinum-containing chemotherapy, treatment with pembrolizumab demonstrated a significant improvement in OS and a clinically meaningful benefit in durable responses compared with standard of care therapies.

In participants with MSI-H tumors, pembrolizumab provided evidence of clinically meaningful benefit over standard treatments, regardless of tumor histology.

For the treatment of gastric or GEJ adenocarcinoma, pembrolizumab administered as a third line or later treatment to participants with PD-L1 positive tumors demonstrated durable response, as assessed by a median ORR and DOR that exceeded the historic data.

Safety Summary

Pembrolizumab has a positive benefit-risk profile and is well tolerated in the approved indications, as evidenced by a low rate of toxicity Grade 3 to 5 drug-related AEs (13.8%), discontinuations due to AEs (11.9%), and deaths due to drug-related AEs (0.4%) in the RSD.

A Phase II, Single-arm Study of Combination Pembrolizumab and Olaparib in the Treatment of Patients with Advanced Cholangiocarcinoma

Version 2.1: 17Mar2023

Furthermore, the frequency of immune-mediated Adverse Events of Special Interest (AEOSI) is low, and these events are readily managed in the clinical setting (see package insert] for guidance on management of immune and non-immune-mediated events of interest). Overall, the safety profile of pembrolizumab as defined by the RSD has remained generally consistent with accrual of additional data and participant exposure as represented by the RCSD.

Conclusion

Participants with a broad range of advanced cancers benefit from pembrolizumab therapy, which can induce high rates of durable responses and benefits in OS that are superior to those seen with standard therapies.

Pembrolizumab has a positive benefit-risk profile and is well tolerated in the approved indications. Furthermore, most AEOSIs are mild to moderate in severity, and are generally readily manageable with appropriate care in the clinical setting (see package insert and section 6.1 for guidance on management).

The safety and efficacy data generated to date provide a favorable benefit-risk assessment for the use of pembrolizumab as a treatment for patients in the approved indications.

4.2.1.3 Dosage and Administration

Pembrolizumab is provided as a white to off white lyophilized powder (50 mg/vial) or as a liquid solution (100 mg/vial) in Type I glass vials intended for single use only. Pembrolizumab Powder for Solution for Infusion, 50 mg/vial, is reconstituted with sterile water for injection prior to use. Pembrolizumab is formulated with L-histidine as buffering agent, polysorbate 80 as surfactant, sucrose as stabilizer/tonicity modifier, and hydrochloric acid (HCl) and/or sodium hydroxide (NaOH) for pH adjustment (if necessary). The drug product is stored as a stable lyophilized powder or liquid solution under refrigerated conditions (2°C - 8°C). The product after reconstitution with sterile water for injection and the liquid drug product is a clear to opalescent solution, which may contain extraneous and proteinaceous particulates. The reconstituted product and liquid product is intended for IV administration. The reconstituted drug product solution and liquid drug product can be further diluted with normal saline in IV containers made of polyvinyl chloride (PVC) or non-PVC material. Reconstituted vials should be immediately used to prepare the infusion solution in the IV bag and the infusion solution should be immediately administered. If not used immediately, vials and/or IV bags may be stored at 2-8 °C for up to a cumulative time of 20 hours. If refrigerated, the vials and/or IV bags should be allowed to equilibrate to room temperature prior to subsequent use. Pembrolizumab solutions may be stored at room temperature for a cumulative time of up to 4 hours. This includes room temperature storage of reconstituted drug product solution and liquid drug product in vials, room temperature storage of infusion solution in the IV bag and the duration of infusion.

A Phase II, Single-arm Study of Combination Pembrolizumab and Olaparib in the Treatment of Patients with Advanced Cholangiocarcinoma

Version 2.1: 17Mar2023

4.3 Olaparib

A PARP inhibitor is a DNA repair inhibitor, and when applied to a tumor that has a DNA repair defect, there is a synergistic effect between the defect and the inhibitor in a process known as “synthetic lethality”, leading to tumor cell death. Development of therapeutics based on this approach is shown to be effective in the treatment of hereditary breast and ovarian cancers, and the U.S. food and Drug Administration has approved two PARP inhibitors—olaparib and rucaparib—to treat certain BRCA-mutant ovarian cancers.

4.3.1 Non-clinical pharmacology

Olaparib is a new chemical entity that is a potent inhibitor of mammalian PARP-1, PARP-2 and PARP-3 and inhibits selected tumor cell lines in vitro and xenograft tumor growth in vivo, either as a stand-alone treatment or in combination with established chemotherapies. Olaparib has an IC₅₀ against the PARP-1 enzyme of 5 nM, an IC₅₀ against the PARP-2 enzyme of 1 nM, and an IC₅₀ against the PARP-3 enzyme of 4 nM. The main target of olaparib that is responsible for the induction of synthetic lethality in HRD cancer cells is PARP-1. In cells cultured in vitro, 50% inhibition of PARP-1 activity, as measured by the formation of PAR, occurs at concentrations of 6-8 nM, with greater than 90% PAR formation being inhibited between 30-100 nM and complete inhibition of PARP-1 activity occurring between 100-300 nM. In vivo, the PARP-1 IC₅₀ was 120 nM (standard error \pm 33 nM) and the IC₉₀ was 576 nM (standard error not calculated). Olaparib doses leading to tumor regression in a BRCA2 mutant PDX model resulted in PARP-1 inhibition of >50% for more than 10 hours and inhibition of >90% for more than 4 hours. Analysis of a panel of cancer cell lines identified those deficient in homologous recombination repair factors, notably BRCA1 and BRCA2, as being particularly sensitive to treatment with olaparib.

The sensitivity of tumor cell lines and PDX models to Olaparib correlates with their sensitivity to platinums, which suggests that the latter can be used as a potential surrogate marker for the former. In sensitive *BRCA*-mutant in vivo models, olaparib extended the anti-tumor activity of platinum agents when given sequentially, suggesting the potential for olaparib to be given as a maintenance treatment following treatment with platinum. Olaparib showed no significant activity when screened in vitro against a diverse panel of molecular targets including enzymes, receptors, transporters and ion channels. Olaparib inhibited the hERG encoded potassium channel in vitro, with an IC₅₀ of 226 μ M. Olaparib showed no significant effects in vivo in dog cardiovascular/respiratory and rat Irwin (behavioral) tests.

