3.3 Exploratory Objective

(1) Objective:

1. To correlate in tumor samples the baseline density of CD3 and CD8 in the tumor interior and invasive margin, the expression of PD-L1, and the clonality of the T-cell repertoire with ORR, DOR, PFS, and OS.
2. To assess in tumor samples the baseline density of CD3 and CD8 in the tumor interior and invasive margin, the expression of PD-L1, and the clonality of the T-cell repertoire at baseline and after three weeks of treatment, and then correlate these assessments with ORR, DOR, PFS, and OS.
3. To compare in tumor samples the density of CD3 and CD8 in the tumor interior and invasive margin, the expression of PD-L1, and the clonality of the T-cell repertoire at three time points: at the time of disease progression, after three weeks of treatment, and at baseline.
4. To correlate in the cholangiocarcinoma tissue the baseline expression of ERCC (DRCC+/-) or the baseline mutation status of IDH1 or 2 (mutant or non-mutant) with ORR, DOR, PFS, and OS.

(2) Hypothesis:

A Phase II, Single-arm Study of Combination Pembrolizumab and Olaparib in the Treatment of Patients with Advanced Cholangiocarcinoma

Version 2.1: 17Mar2023

Given the low expression of the ERCC1 protein in the majority of cholangiocarcinomas, together with relative frequent IDH1/2 mutations found in these tumor types, we hypothesize that the combination of PARP inhibition and immune checkpoint blockade will produce a durable anti-tumor response against cholangiocarcinoma by synergistically inducing DNA damage, increasing tumor antigen number and producing durable immune response against cholangiocarcinoma. Therapies that target the programmed death-1 (PD-1) receptor have shown unprecedented rates of durable clinical responses in a sub-group of patients with various cancer types [1-5]. Biomarkers in patient tumor that will predict response to anti-PD-1 therapy are being actively investigated. One mechanism by which cancer tissues limit the host immune response is via upregulation of PD-1 ligand (PD-L1) and its ligation to PD-1 on antigen-specific CD8+ T cells [6, 7]. Recent research has reported that tumor regression after therapeutic PD-1 blockade requires pre-existing CD8+ T cells that are negatively regulated by PD-1/PD-L1-mediated adaptive immune resistance [8].

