There has been much interest in the combination of PARP inhibitors and immunotherapy, based on preclinical data that support the association of BRCA1/2 mutational status with neoantigen load, tumor infiltrating lymphocytes, and the expression of PD-1/PD-L1 or CTLA-4, thus forming the rationale for combination therapy. There have been data indicating that BRCA1/2 deficient cancers express higher levels of neoantigens and are therefore likely to be more immunogenic. In addition, preclinical studies showed that a combination of PARP inhibition with a CTLA-4 antibody had synergistic activity against BRCA1/2 mutant ovarian cancer [24]. A crosstalk between PARPi and tumor-associated immunosuppression, and provides evidence to support the combination of PARPi and PD-L1 or PD-1 immune checkpoint blockade [25]. PARPi-related upregulation of PD-L1 expression in breast cancer cell lines and animal models appeared to occur via an induction of high GSK3 β Ser9 phosphorylation (the inactive form of GSK3 β). Thus, knocking out GSK3B β activity significantly increased PD-L1 expression. However, PD-L1 expression in GSK3 β -knockout cells was no longer enhanced by PARPi (olaparib) treatment. These results suggested that inactivation of GSK3 β is required for the PARPi-induced PD-L1 upregulation. PARPi attenuated antitumor immunity via upregulation of PD-L1 increased PD-1 binding, which was resistant to activated T-cell killing. Blockade of PD-L1 acted to resensitize PARPi-treated cancer cells to T-cell killing. The data supports the hypothesis that the combination of a PARPi and an immune checkpoint inhibitor is a potential therapeutic approach to cancer treatment.

4.4.1.1 Rationale for the combination of olaparib and pembrolizumab in cholangiocarcinoma:

Research into the molecular pathogenesis of cholangiocarcinoma has revealed potential mechanisms contributing to tumorigenesis. Low expression of excision repair cross complementation group 1 (ERCC1) is found in 74% of cholangiocarcinomas, and this is associated

A Phase II, Single-arm Study of Combination Pembrolizumab and Olaparib in the Treatment of Patients with Advanced Cholangiocarcinoma

Version 2.1: 17Mar2023

with susceptibility to PARP inhibition [26]. In addition, mutations in isocitrate dehydrogenase-1 or -2 (IDH1/2) are found in 25% of cholangiocarcinomas. [27].

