8.1.1.3 Sample Size and Accrual

The primary objective of the study is to assess the ORR of patients with advanced cholangiocarcinoma receiving a combination of pembrolizumab and olaparib. It is hypothesized that the combination of olaparib and pembrolizumab will improve the overall response rate (ORR) from 17.5% (historical control) to 35% in patients with advanced cholangiocarcinoma. The sample size is based on the number of patients that are anticipated to complete the primary objective.

Simon's two-stage Optimum design will be used to test the null hypothesis of $P \leq 0.05$ versus the alternative hypothesis of $P \geq 0.25$. At the first stage, 13 patients will be treated with the combination of olaparib and pembrolizumab. The trial will be terminated if 2 or fewer patients respond. If there are more than 2 responses, the trial will go on to the second stage and 20 more patients will be enrolled to a total of 33 patients. If the total number responding among the 33 patients is ≤ 8 , the null hypothesis will not be rejected and the combination of olaparib plus pembrolizumab will not be investigated further. Using this statistical method, there is a 0.092 (9.2%) probability of erroneously concluding that this drug combination is effective when it actually is not (targeted value of 0.1). If the drug is actually effective, there is a 0.192 probability of concluding that it is not (targeted value of 0.2). The power of the design is 85% with a one-sided significance level of 0.05. If we assume a 10% patient dropout rate, then a total of 36 patients will be needed for the trial.

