The expression of ERCC (DRCC+/-), and the mutation status of IDH1 or 2 (mutant or non-mutant) in the same cholangiocarcinoma tissue at baseline will be summarized using descriptive statistics (N, frequency). The response of ERCC- or IDH1/2 wild type tumors at baseline will be compared with the response of ERCC+ or IDH1/2 mutant tumor using Chi-Square test or Fisher's exact test when appropriate. The relationship between these biomarker levels and the DOR and PFS will be explored via Kaplan-Meier methodology and Log-rank test.

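### BRCA1/2 (homologous-recombination) status, which the rationale ties to benefit from both drugs, is never recorded, so the trial cannot show whether a few carriers drove a result near 9/33 or diluted the ERCC1 and IDH1/2 contrasts

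*Combined protocol and SAP*

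**What the plan says.** The rationale relies on BRCA/HR deficiency in four places.

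- Section 4.3 explains PARP inhibition by synthetic lethality in tumours with a DNA-repair defect. Its clinical example is BRCA-mutant ovarian cancer.
- Section 4.3.1 reports that a cell-line panel "identified those deficient in homologous recombination repair factors, notably BRCA1 and BRCA2, as being particularly sensitive to treatment with olaparib".
- Section 4.4.1 says there are data that "BRCA1/2 deficient cancers express higher levels of neoantigens and are therefore likely to be more immunogenic".
- Section 4.4.1.1 supports IDH1/2 as a marker because IDH-mutant tumours behave like BRCA-mutant ones.

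The planned repair markers are narrower. The response objective in 3.3 uses "the baseline expression of ERCC (DRCC+/-) or the baseline mutation status of IDH1 or 2 (mutant or non-mutant") and nothing else on DNA repair. Section 8.2.3 states the test as: "The response of ERCC- or IDH1/2 wild type tumors at baseline will be compared with the response of ERCC+ or IDH1/2 mutant tumor".

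BRCA or HR-gene status does not appear in eligibility (5.2, 5.3), the flow chart (6.1), disease details and prior treatment (7.1.1.5), tissue and blood studies (7.1.2.7), endpoints (8.1.1.2) or analysis (8.2). The sequencing described in 7.1.2.7.1 is of the T-cell receptor. Section 7.1.2.7.4 stores leftover specimens, so later testing is possible but not planned.

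**The concern.** The trial measures a stand-in for BRCA-like biology (IDH1/2) but not BRCA itself. Two readings of the result are affected.

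First, the primary decision turns on 9 responders of 33. If the count lands near that line, readers will ask whether a few HR-deficient tumours supplied the margin and whether the finding carries over to patients without such a defect. The planned data cannot answer. A split chosen after responses are known would be post hoc.

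Second, a BRCA-mutant tumour with normal ERCC1 or wild-type IDH is placed in a group that the protocol expects to be less sensitive to olaparib. If it responds, it pulls that marker contrast toward no difference.

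**Working it through.** **Step 1. Reproduce the plan's own figures (8.1.1.3).** Inputs: improvement "from 17.5% (historical control) to 35% in patients with advanced cholangiocarcinoma"; a stage 1 size of 13, with the stopping rule "The trial will be terminated if 2 or fewer patients respond"; 20 more patients to 33; 8 or fewer responders means the null is not rejected.

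P(go) = sum over x > 2 of P(X1 = x) × P(X2 > 8 − x), with X1 ~ Bin(13, p) and X2 ~ Bin(20, p).

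- p = 0.175: P(go) = 0.0922 (stated 0.092).
- p = 0.35: P(go) = 0.8084, so type II error is 0.1916 (stated 0.192).

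Both reproduce. The null of 0.05 and alternative of 0.25 printed in the same section do not fit this rule (0.00002 and 0.39). That is a separate inconsistency; 17.5%/35% is used here.

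**Step 2. Effect of carriers on the pooled ORR.** Carrier share f and carrier response r are not in the documents, so both are assumptions. Non-carriers are held at 17.5%. Pooled ORR = f·r + (1 − f)·0.175, put through the same rule:

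| f (carriers in 33) | r | True ORR | P(go) |
|---|---|---|---|
| 0 | – | 17.5% | 0.092 |
| 3% (1.0) | 40% | 18.2% | 0.111 |
| 6% (2.0) | 50% | 19.5% | 0.151 |
| 10% (3.3) | 60% | 21.8% | 0.240 |
| 10% (3.3) | 100% | 25.8% | 0.428 |

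The last row is an extreme bound. For carriers alone to lift the ORR from 17.5% to 35%, f would have to be (0.35 − 0.175)/(r − 0.175). That is 54% at r = 50% and 21% even if every carrier responds.

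**Step 3. Carriers in the marker-negative groups.** Section 4.4.1.1 gives 74% low ERCC1 and 25% IDH1/2 mutant. Of 33 patients:

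- ERCC1-normal: 33 × 0.26 = 8.6
- IDH wild type: 33 × 0.75 = 24.8
- Both: 33 × 0.26 × 0.75 = 6.4, assuming independence

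At an assumed f = 5%, the chance of at least one carrier, 1 − 0.95^m, is 0.37 (m = 9), 0.72 (m = 25) and 0.26 (m = 6).

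In the smallest group, replacing one non-carrier by one carrier shifts the expected ORR by (0.40 − 0.175)/6.4 = 3.5 points at r = 40%, and by (0.60 − 0.175)/6.4 = 6.6 points at r = 60%.

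**Step 4. Power of the marker contrasts.** Assume 50% response in marker-positive and 17.5% in non-carrier marker-negative patients, Fisher's exact test, two-sided 0.05. With no carriers, power is 0.33 (ERCC1, 24 v 9) and 0.41 (IDH, 8 v 25). If f = 5% in the comparator and carriers respond at 80-100%, with the marker-positive group held at 50%, power falls to 0.25-0.26 and 0.31-0.33.

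**Step 5. How not to adjust.** Take non-carrier response of 35% (marker-positive) and 17.5% (comparator), f = 10% in both groups and r = 60%.

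- Non-carrier difference: 35 − 17.5 = 17.5 points.
- Unadjusted: (0.9 × 35 + 0.1 × 60) − (0.9 × 17.5 + 0.1 × 60) = 37.5 − 21.75 = 15.75 points.
- Carriers removed from the comparator only: 37.5 − 17.5 = 20.0 points.

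One-sided removal overshoots by 2.5 points, more than the 1.75-point dilution it is meant to cure.

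**The case against.** The case for leaving the plan alone is substantial, and most of it stands as a limit on what may be claimed.

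- A reader might infer that the protocol treats BRCA status as the main determinant of olaparib benefit. It does not. The sensitivity statement concerns cell lines, the approval cited is in ovarian cancer, and the rationale specific to cholangiocarcinoma is ERCC1 and IDH1/2.
- A reader might infer that carriers inflate the ORR, or raise the false-positive rate from 9.2% to as much as 24%. Section 4.5.2 defines ORR over all subjects and eligibility has no molecular selection, so carriers' responses are part of the effect being estimated. In Step 2 the pooled ORR exceeds 17.5%, so the null is false and P(go) is power against a small real effect. Nothing says that the historical 17.5% excludes carriers, or that this trial over-represents them.
- A reader might infer that one carrier moves the comparator ORR by 16 points (1/6.4). That sets a certain responder against a certain non-responder; the expected shift is 3.5-6.6 points. Nor is the 6.4-patient group clearly a planned response comparator. The combined grouping in 4.5.3 concerns immune markers, and 3.3 reads most naturally marker by marker.
- Carriers may fall in either marker group. If they are spread evenly and respond equally, the contrast shrinks only by the factor 1 − f, that is by 3-10% of its size, in an exploratory analysis already short of power.
- The yield is small: about 1-3 carriers, with status missing for some patients.

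These points rule out a claim of bias in the primary test. They do not supply the missing information: general collection of disease details does not name BRCA, and stored tissue with no plan attached does not give a pre-specified split.

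**Conclusion.** The gap is real and modest. The rationale rests partly on BRCA/HR deficiency, and the plan never records it, so a result near 9/33 cannot be described by this factor and the ERCC1 and IDH contrasts carry an unmeasured covariate that can dilute them.

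Under the assumed 3-10% carriers responding at 40-60%, with non-carriers at 17.5%, the true ORR is 18.2-21.8% and P(go) is 0.11-0.24. These figures depend wholly on inputs that the documents do not give. They bear on how far a positive result generalises, not on type I error. The primary estimand, sample size and decision rule need no change on this account.

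**What to change.** 1. **Section 7.1.1.5.1:** record BRCA1/2 and other HR-gene status from any existing tumour or germline report, as mutant, wild type or unknown. No new test is required.
2. **Section 8.2.1:** keep the all-patient ORR as primary and add a descriptive ORR by known status.
3. **Section 8.2.3:** show known carriers as a separate stratum, or exclude them from both marker groups in a sensitivity analysis; never from the comparator alone (Step 5). Separately, reconcile the grouping there, which pairs ERCC-negative with IDH wild type, with 3.3 and 4.5.3, where low ERCC1 goes with IDH mutant.

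The cost is one CRF field and a few table rows, with no added visit or procedure. Status will be unknown for some patients, perhaps not at random, and carriers will be few, so the output is a descriptive sensitivity check and should be labelled as such.
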